Attention deficit/hyperactivity disorder (ADHD) is associated primarily with debilitating levels of inattention, hyperactivity, and impulsivity. Psychostimulant medications such as Vyvanse (lisdexamfetamine, LDX) are the first-line treatment of ADHD; however, many children with ADHD are treated with non-stimulant medications, such as alpha-2 agonists. Extended-release guanfacine (GXR), an alpha-2 agonist, is FDA approved for the treatment of ADHD in children.

Whereas MRI studies have examined the effects of psychostimulant treatment such as LDX on the structure and function of the brain, very limited data are similarly available on GXR effects. Interestingly, whereas LDX is thought to alleviate ADHD symptoms through its effects on dopaminergic and noradrenergic pathways, alpha-2 agonists, like GXR, are specific to noradrenergic pathways.

Combining MRI with a pharmacological trial of either LDX or GXR, we aim to examine the effects these treatments, which exhibit differing mechanisms of action, on neural circuits underlying cognitive control. Our goals are to examine and compare the effects of treatment with LDX or GXR on circuit abnormalities, to test whether engagement of target neural circuits (i.e., cognitive control circuits) results in symptom reduction (i.e., reduced impulsivity), and to explore predictors of treatment response. We will examine treatment effects using multiple units of analysis (neuroimaging, clinical interviews, and self- and parent-reports).

Developing a better understanding of how existing treatments lead to symptom improvement should facilitate the development of more effective treatments with fewer side effects.

Specific Aims and Hypotheses

Specific Aims and Hypotheses

Aim: To determine and compare the changes in brain structure and function that LDX and GXR treatment produce in patients with ADHD.

Hypothesis 1a: Before treatment, ADHD participants compared with healthy controls will have (i) significantly reduced volumes in the prefrontal cortex, (ii) altered connectivity between the prefrontal cortex and basal ganglia and (iii) reduced prefrontal task-related activation (fMRI signal) on an fMRI task of impulse control.

Hypothesis 1b: Following 6 weeks of treatment with either LDX or GXR, MRI measures of the prefrontal cortex will change to become more similar to those of healthy control participants.

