Healthy control participants and participants with possible ADHD may be recruited from Protocol #7549 into this protocol. To minimize participant burden, we may share de-identified data collected under Protocol #7549 with this protocol, and vice versa. For example, we may share information collected as part of the lifetime diagnostic interview between the two protocols so that participants do not need to repeat this lengthy assessment and can instead provide an update on their mental health. Otherwise, assessment and MRI scanning procedures differ between this protocol and Protocol #7549; therefore healthy control participants will be assessed and scanned separately for each of these protocols.

Inclusion/Exclusion Criteria

Name the subject group/sub sample

Children with ADHD

Create or insert table to describe the inclusion criteria and methods to ascertain them

ADHD Participants	Methods of Ascertainment
1. The participant satisfies DSM-5 criteria for a primary diagnosis of ADHD, any subtype.	1. K-SADS administered by research staff (BA level or higher).
2. Participants must provide assent and a legal guardian must provide consent.	Interview, Staff Doctors
3. The participant is male or female 6 - 17 years of age and in good physical health.	Interview, Staff Doctors
4. Girls of childbearing potential must have a negative urine pregnancy test and must be using adequate contraception.	Urine pregnancy test performed by Study Staff; Interview, Staff Doctors
5. English Speaking.	Telephone Screening Questionnaire

Create or insert table to describe the exclusion criteria and methods to ascertain them

ADHD Participants	Methods of Ascertainment
1. The potential participant has a comorbid Axis I psychiatric diagnosis or other symptomatic manifestations that, in the opinion of the examining physician, will contraindicate LDX or GXR treatment or confound safety assessments.	Medical history by Staff Doctors
2. The potential participant meets DSM-5 criteria for active substance abuse and/or dependence.	K-SADS, interview by Staff Doctor
3. The potential participant is currently taking, or has taken within the past 4 months, a psychotropic medication.	Medical history by Staff Doctors
4. The potential participant has a documented allergy or intolerance to LDX or GXR products.	Medical history by Staff Doctors

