5. The subject has a medical condition or family history of a medical condition (e.g., cardiovascular disease) that may interfere with study participation, or for which treatment with LDX or GXR may pose a risk to the subject.	Medical history by Staff Doctors
6. The potential participant is pregnant or lactating.	Medical history performed by Staff Doctors; Urine pregnancy test performed by Study Staff
7. The potential participant is actively suicidal *	Medical history performed by Staff doctors. Columbia Suicide Severity Rating Scale (C-SSRS) administered by Staff Doctor.
*If a participant is deemed to be actively suicidal, appropriate measures will be taken which may include escorting the participant to the emergency room and/or consulting with the participant's referring clinician.	
8. MRI contraindications (e.g., irremovable metal on the body, pacemaker, braces, etc.)	MRI Safety Questionnaire. Administered by study staff.
9. Full Scale IQ < 70.	WASI. Administered by study staff (BA level or higher).
10. History of seizure (except febrile seizure)	Medical history by

Staff Doctors

Inclusion/Exclusion Criteria #2

Name the subject group/sub sample

Healthy Control Children

Create or insert table to describe the inclusion criteria and methods to ascertain them

Healthy Controls	Methods of Ascertainment
1. The participant does not meet criteria for a DSM-5 disorder.	K-SADS administered by research staff (BA level or higher)
2. Participants must provide assent and a legal guardian must provide consent.	Interview by research staff (BA level or higher)
3. The participant is male or female 6 - 17 years of age	Interview by research staff.
4. Girls of childbearing potential must have a negative urine pregnancy test.	Urine pregnancy test performed by Study Staff.
5. English Speaking.	Telephone Screening Questionnaire

Create or insert table to describe the exclusion criteria and methods to ascertain them

Healthy Controls	Methods of Ascertainment
1. The potential participant meets DSM-5 criteria for active substance abuse and/or dependence	K-SADS administered by research staff (BA level or higher)
2. The potential participant is currently taking a psychotropic medication.	Telephone Screening Questionnaire
3. The potential participant has a history of a serious medical illness.	Telephone Screening Questionnaire

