pre-post change in cognitive control or reward processing circuits as primary predictors, while controlling for baseline impulsivity and treatment group. The mediation effect is then estimated by taking the product of the estimates for **path a and b** and using the bootstrap method to obtain standard errors, confidence intervals, and the test for statistical significance.

To test whether treatment effects on cognitive control or reward processing circuits are specific in mediating improvements in impulsivity, we will explore whether treatment-related changes in other neural networks also mediate the effect of treatment on impulsivity. We will first screen these additional neural networks based on a significant effect of treatment on connectivity within these networks. Only networks that show significant change with treatment will be added to the multiple mediation analyses described above. The indirect effects of the cognitive control or reward processing circuits will be tested in the existence of the mediation effects of other neural networks using the bootstrapping method.

Power: Power for detecting the mediation effect depends on the size of the associations between (a) treatment group and changes in cognitive control and reward processing circuits, and (b) changes in cognitive control and reward processing circuits and changes in impulsivity. Based on tabulated recommendations for sample sizes needed to test mediation effects, with a sample size of $n=60$, we have more than 80% power to detect a significant mediation effect with medium effect size of both paths a and b.

Secondary Objective: ADHD patients with baseline MRI anomalies within reward processing circuits will respond to Vyvanse, but not Intuniv, treatment. Conversely, ADHD patients with baseline MRI anomalies that are circumscribed to cognitive control circuits (i.e., reward processing comparable to healthy controls) will predict response to either Intuniv or Vyvanse.

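### Healthy controls have no look-back for psychotropic use, while children with ADHD have a 4-month one, so a recently medicated child could enter the reference group for Hypotheses 1a and 1b

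*Protocol*

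**What the plan says.** Protocol, Inclusion/Exclusion Criteria, Children with ADHD, exclusion 3: "The potential participant is currently taking, or has taken within the past 4 months, a psychotropic medication". It is ascertained from a medical history taken by staff doctors.

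Protocol, Inclusion/Exclusion Criteria #2, Healthy Control Children, exclusion 2: "The potential participant is currently taking a psychotropic medication". It is ascertained from the telephone screening questionnaire.

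The control criterion closest to filling the gap is inclusion 1, assessed by K-SADS: "The participant does not meet criteria for a DSM-5 disorder". It does not say whether current or lifetime disorder is meant.

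Controls are the comparator in both hypotheses under Specific Aims and Hypotheses. Hypothesis 1a is the baseline contrast ("Before treatment, ADHD participants compared with healthy controls will have" is how it opens). Hypothesis 1b predicts that after treatment "MRI measures of the prefrontal cortex will change to become more similar to those of healthy control participants". Under Concurrent Research Studies, control data may also be pooled from Protocols #6573 and #7261R, whose medication criteria are not given.

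**The concern.** This study asks how psychotropic drugs change brain measures. Recent drug exposure in the comparator group is therefore a version of the exposure under study, and the plan limits it on one side of the ADHD-control comparison only. Read literally, control exclusion 2 passes a child who stopped a psychotropic drug the day before screening. If such children are enrolled, the control mean may not represent unexposed, unaffected children. The baseline difference (1a) and the distance still to be closed after treatment (1b) would then be measured against a shifted reference.

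**Working it through.** **Step 1: does another control criterion close the gap?** The remaining control criteria cover these matters:

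- Consent and assent, age, English and pregnancy testing: none concerns past medication.
- Exclusion 1, active substance abuse or dependence: not past prescribed medication.
- Exclusion 3, history of serious medical illness: catches some children treated for a medical reason, but not those whose condition was not serious.
- Exclusions 4 to 7 (pregnancy or lactation, MRI contraindications, IQ below 70, seizure): not past medication as such.
- Inclusion 1, no DSM-5 disorder: catches any child who still meets criteria. It also catches remitted cases if it is applied as lifetime. It does not catch a child treated for a non-psychiatric indication.

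Two routes stay open: a non-psychiatric indication, and a remitted disorder if inclusion 1 means current disorder only.

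**Step 2: which analyses use controls?**

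- Hypotheses 1a and 1b: yes. The lay summary adds that the post-treatment scans will be compared with the controls' scans.
- SAP primary objective, Time by Treatment model: the between-group factor has two levels, LDX and guanfacine. No controls.
- SAP mediation model: treatment, circuit change and impulsivity change in treated children. No controls.
- SAP secondary objective, moderation regression: the outcome is pre-post change in impulsivity. Controls have a baseline visit only, so they cannot contribute.

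**Step 3: how large could it be?** The documents give no figure to reproduce. They state neither how many controls are affected nor any carry-over effect. What follows is illustration.

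Assume k of n controls are each shifted by d SD. The control mean then moves by (k/n) × d. Take k = 1 to 3 and d = 0.3 to 0.8 (both assumed). Take n = 30 (completers, Description of Subject Population, Sample #2) or n = 10 (Lay Summary).

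| n | smallest shift | largest shift |
|---|---|---|
| 30 | (1/30) × 0.3 = 0.01 SD | (3/30) × 0.8 = 0.08 SD |
| 10 | (1/10) × 0.3 = 0.03 SD | (3/10) × 0.8 = 0.24 SD |

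For scale, the standard error of the ADHD-control difference, with 30 ADHD children, is √(1/30 + 1/30) = 0.258 SD with 30 controls and √(1/30 + 1/10) = 0.365 SD with 10. The largest shifts are 0.08/0.258 = 0.31 and 0.24/0.365 = 0.66 standard errors.

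**Step 4: an unfavourable case.** Suppose each affected control sits at the ADHD mean, so the difference is multiplied by (1 − k/n). Set the true difference to the value with 80% power (two-sided 5%, normal approximation): (1.960 + 0.842) × 0.258 = 0.723 SD with 30 controls, and (1.960 + 0.842) × 0.365 = 1.023 SD with 10.

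| affected controls | power, 30 controls | power, 10 controls |
|---|---|---|
| 0 | 80% | 80% |
| 1 | 77% | 71% |
| 2 | 74% | 61% |
| 3 | 71% | 50% |

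This fixes the direction towards the ADHD group. With 10 controls it also takes a shift (1.02 SD) above the range in step 3. It should not be read as an expected loss.

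**The case against.** **Different windows need not be an error.** Children with ADHD enter a drug trial with titration and controls do not, so the stricter rule may serve the treatment phase. A reader might infer that the 4 months are there to secure an unmedicated baseline scan, but the protocol states no purpose. This stands. It means the difference needs a reason or a match; it does not show that the comparison is sound without one.

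**Inclusion 1 probably removes most such children.** It is not limited to current disorder, whereas neighbouring criteria do use words for current status. Under Study Procedures, the diagnostic interviews cover past as well as current psychiatric history, and telephone screening asks about psychiatric history and rates ADHD symptoms. This largely stands, and it makes a recently treated ADHD child an unlikely control. It does not reach the non-psychiatric indication, and collecting a history is not the same as excluding on it.

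**The direction is not known.** A reader might infer that affected controls shrink the ADHD-control difference. The documents do not support that. Hypothesis 1b expects treatment to move measures towards controls, so carry-over from a drug and residue of an illness could pull in different directions.

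**The reach is limited.** A reader might infer from the SAP secondary objective's phrase "reward processing comparable to healthy controls" that control data also drive the moderation result. The regression actually specified uses baseline region-of-interest measures, Group and their interactions, with no control-derived cut-off. This stands.

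**Conclusion.** The asymmetry is plain in the text and unexplained. It leaves a narrow route by which a recently medicated child can become a healthy control, and it bears on Hypotheses 1a and 1b only. The effect is probably small: at most 0.08 SD on the control mean with 30 controls, and 0.24 SD only if three of ten are affected. Both figures rest on assumed numbers affected and assumed shifts. This is a worthwhile low-cost improvement, not a flaw that threatens the randomised comparison. The continuation application reports 38 of 160 enrolled, leaving 122 of the approved places, though it does not split these by group.

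**What to change.** - **Controls still to be enrolled:** replace exclusion 2 with the wording of ADHD exclusion 3, or state why the windows differ. Ascertain it from the past history already taken at the diagnostic interview, or from the staff doctors' medical history already listed for control exclusions 4 and 7. Telephone screening runs under Protocol #7096, so relying on that call alone could mean amending a second protocol.
- **Inclusion 1:** say whether it means current or lifetime disorder.
- **Pooled controls:** apply the same medication rule when selecting from #6573 and #7261R.
- **Controls already scanned:** record past medication where it is available, and identify those who fail the rule without sight of imaging results. Report the ADHD-control comparisons with and without them. Simply dropping them would be a post hoc exclusion, and the documents do not show whether the screening records hold the information.

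**Cost:** one reworded criterion, one added screening question, and perhaps one or two controls lost. At the differences used in the last working step, losing two controls without replacement leaves 79% power with 28 (0.723/√(1/30 + 1/28) − 1.960 = 0.79) and 73% with 8 (1.023/√(1/30 + 1/8) − 1.960 = 0.61). With enrolment open, they can be replaced.

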8-19-19 IVY Healthy Control Google Ad.pdf

Upload copy(ies) of unbolded Assent Form(s)

6-29-20 IVY Assent HC noBOLD.pdf

6-29-20 IVY Assent ADHD noBOLD.pdf

Upload copy(ies) of bolded Assent Form(s)

Upload copy(ies) of the HIPAA form

IVY HIPAA Child.pdf

Upload any additional documents that may be related to this study

2-28-18 IVY MRI Letter - No Finding CHILD.pdf

2-28-18 IVY MRI Letter - Significant CHILD.pdf

2-28-18 IVY MRI Letter - Uncertain CHILD.pdf

4-27-20 IVY Parent Recruitment Letter - noBOLD.pdf

4-27-20 IVY Parent Recruitment Letter - BOLD.pdf

4-27-20 Metro Newspaper Advertisement - noBOLD.pdf

4-27-20 Metro Newspaper Advertisement - BOLD.pdf

3-27-19_GFS_Telephone_Script_noBOLD.pdf

Title: An fMRI Study of Stimulant vs. Non-Stimulant Treatment of ADHD

NCT Number: NCT02259517

Document Date: July 10, 2020

Hypothesis Testing

Primary Objective: Vyvanse (lisdexamfetamine; LDX) reduces impulsivity by normalizing cognitive control and reward processing circuits, whereas Intuniv (guanfacine, extended-release; G-EX) reduces impulsivity by normalizing cognitive control but not reward processing circuits.

We will first examine whether there are significant pre- vs. post-treatment changes in cognitive control and reward processing circuits. **Task-based functional MRI (fMRI) analyses:** We will enter each participant's task-related contrast map into a 2×2 repeated measures factorial model, treating Time as a repeated measure with two levels (pre- and post-treatment), and Treatment as a between group factor with two levels (LDX and G-EX). We will isolate an interaction term (Time \times Treatment) to determine differential effects of treatment on task-related activation and then conduct post-hoc t- tests to determine the nature of the interaction. **Resting-state functional connectivity MRI (Rs-fcMRI) and Diffusion Tensor Imaging (DTI):** Analyses will be similar to those for task-based fMRI, but dependent variables will be seed based connectivity and FA maps.

For mediation analysis of treatment effects, we first estimate the changes in cognitive control and reward processing circuits that result from treatment (described in paragraph above). We then establish that the changes in these circuits, in turn, affect impulsivity, while controlling for treatment group. To estimate **path a (Fig. 1)**, we will use a linear regression model with pre-post

[figure not shown]

Figure 1 Mediation Model

changes in cognitive control and reward processing circuits as the outcome variable and treatment as the predictor variable. If we find a significant effect of treatment on both reward and cognitive control circuits, we will pursue multiple mediation analyses; otherwise, we will include only the circuit in which there is a significant effect of treatment. To estimate **path b**, we will use a linear regression model with pre-post change scores in impulsivity (based on parent report) as the outcome and

pre-post change in cognitive control or reward processing circuits as primary predictors, while controlling for baseline impulsivity and treatment group. The mediation effect is then estimated by taking the product of the estimates for **path a and b** and using the bootstrap method to obtain standard errors, confidence intervals, and the test for statistical significance.

To test whether treatment effects on cognitive control or reward processing circuits are specific in mediating improvements in impulsivity, we will explore whether treatment-related changes in other neural networks also mediate the effect of treatment on impulsivity. We will first screen these additional neural networks based on a significant effect of treatment on connectivity within these networks. Only networks that show significant change with treatment will be added to the multiple mediation analyses described above. The indirect effects of the cognitive control or reward processing circuits will be tested in the existence of the mediation effects of other neural networks using the bootstrapping method.

Power: Power for detecting the mediation effect depends on the size of the associations between (a) treatment group and changes in cognitive control and reward processing circuits, and (b) changes in cognitive control and reward processing circuits and changes in impulsivity. Based on tabulated recommendations for sample sizes needed to test mediation effects, with a sample size of $n=60$, we have more than 80% power to detect a significant mediation effect with medium effect size of both paths a and b.

Secondary Objective: ADHD patients with baseline MRI anomalies within reward processing circuits will respond to Vyvanse, but not Intuniv, treatment. Conversely, ADHD patients with baseline MRI anomalies that are circumscribed to cognitive control circuits (i.e., reward processing comparable to healthy controls) will predict response to either Intuniv or Vyvanse.

We will test the moderation effect of the baseline MRI measures cognitive control and reward processing circuits on the treatment response. We will use linear regression models with pre-post change scores in impulsivity measures as outcomes and Group, baseline measures of cognitive control and reward processing circuits measured in predefined regions of interest (ROIs), and their interactions as predictors. Likelihood ratio tests will be used to test the effect of moderation with combination of multiple brain imaging measures.

Power: With sample size of $n=60$, the minimum detectable effect size of Cohen's f^2 is 0.09 (smaller than medium effect size 0.15) with 80% power for a two-sided test at the 5% significance level. If the effect size of interactions between baseline measures within cognitive control and reward processing circuits and Group is greater than f^2 is 0.09, we would be able to detect such effect size.

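### The SAP's tests compare change between two active drugs and contain no healthy controls, so they cannot support the normalizing claimed in the primary objective and Hypothesis 1b

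*SAP*

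**What the plan says.** - **SAP, Primary Objective.** LDX "reduces impulsivity by normalizing cognitive control and reward processing circuits"; guanfacine is said to do so for cognitive control but not for reward. Both drugs are therefore expected to act on cognitive control.
- **Protocol, Specific Aims and Hypotheses.** Hypothesis 1b predicts that after six weeks on either drug "MRI measures of the prefrontal cortex will change to become more similar to those of healthy control participants". Hypothesis 1a gives the expected baseline differences from controls: "significantly reduced volumes in the prefrontal cortex", connectivity that differs (no direction stated), and lower prefrontal task activation (direction stated).
- **Protocol, Lay Summary.** Scans are to be compared between children with and without ADHD at baseline, and the second ADHD scans are to be compared with the controls' scans. No measure, contrast or criterion is given.
- **SAP, imaging model.** The text opens with "We will first examine whether there are significant pre- vs. post-treatment changes in cognitive control and reward processing circuits". The model is Time by "Treatment as a between group factor with two levels (LDX and G-EX"). The analyst isolates the interaction and will "then conduct post-hoc t- tests to determine the nature of the interaction". Resting connectivity and FA follow the same scheme.
- **SAP, mediation.** Path a regresses circuit change on treatment. A circuit enters the mediation model only if treatment has a significant effect on it. Path b regresses change in impulsivity on circuit change, adjusted for baseline impulsivity and treatment.
- **SAP, Secondary Objective.** This holds the SAP's only mention of controls: patients with "reward processing comparable to healthy controls". The model that follows uses Group and "baseline measures of cognitive control and reward processing circuits measured in predefined regions of interest (ROIs), and their interactions as predictors", with no control reference.

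**The concern.** Normalizing is a statement about distance to a reference group: the circuit was abnormal and has moved toward the control value. The Protocol collects the reference scans and says they will be used, but the SAP has no term, contrast or definition that uses them. Followed as written, the SAP can show that the two arms differ in change and that change goes with impulsivity. It would report a shift in a circuit that was never abnormal in the same way as a restored one. The word that defines the primary objective and Hypothesis 1b would then rest on no test.

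A second difficulty is that the predicted effect on cognitive control is shared by both drugs, while the interaction and the gate into mediation look only for a difference between them.

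**Working it through.** The SAP gives power figures for mediation and moderation only, and none for a control comparison. There is thus no stated figure to reproduce on this point.

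**1. Where controls could enter.**

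| SAP test | Children analysed | What is tested | Uses control mean? |
|---|---|---|---|
| Time effect | both ADHD arms | average change over the arms | no |
| Time × Treatment; path a | both ADHD arms | difference in change between arms | no |
| Path b | both ADHD arms | association of circuit change with impulsivity change | no |
| Moderation | both ADHD arms | Group × baseline measure | no |

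**2. Why change does not identify normalisation.** Let M0 and M1 be an arm's means before and after treatment, and C the control mean. Change is M1 − M0, which does not contain C. Normalisation needs |M1 − C| < |M0 − C|, which does. In one simulated data set (15 per arm, interaction t = 3.54, p = 0.001) the LDX mean went from −0.51 to +0.21 SD. With C = 0 the gap falls from 0.51 to 0.21. With C = −1 it rises from |−0.51 + 1| = 0.49 to |0.21 + 1| = 1.21. The p-value is the same.

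**3. The shared effect on cognitive control.** If both arms change equally, the difference is zero and the interaction is significant in about 5% of studies. In simulation at n = 60, path a was significant in about 6% and the indirect effect in 4–7%, depending on the bootstrap method. The gate would usually exclude the circuit. The Time effect does respond: if both arms shift by 0.5 SD, its power is 75% (15 per arm) or 97% (30 per arm). It is an average and does not show either arm alone.

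**4. Size of the ambiguity.**
- Inputs from the documents: 15 per arm (30 ADHD children, 1:1; Protocol, Lay Summary and Randomization Procedures), or 30 per arm if the SAP's n = 60 are all randomised children.
- Assumed, because the documents give neither: a shift of 0.5 SD in one arm and retest correlation r = 0.5. There is no true baseline abnormality.
- SD of change = √(2(1 − r)) = 1. The paired-t noncentrality is 0.5√15 = 1.94 (14 df), power 44%; or 0.5√30 = 2.74 (29 df), power 75%.
- If the arm is tested only after a significant interaction, both are significant in about 22% or 45%.
- For r from 0.4 to 0.8, the ungated figures are 38–81% and 68–99%; the gated figures are 18–53% and 38–85%.

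**5. How the reading rule under the fix behaves.** Simulated for one arm and one measure, r = 0.5, equal SDs, no dropout, no pooled controls. Each rate is the percentage of studies in which normalisation would be claimed. The half-width is for one arm's post-treatment gap, t·√(1/n₁ + 1/n₂); for 15 against 10 it is 2.069 × 0.408 = 0.84 SD.

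| Per arm / controls | No deficit, shift 0.5 | Deficit 0.8, no change | Deficit 0.8, shift 0.5 toward controls | 95% half-width (SD) |
|---|---|---|---|---|
| 15 / 10 | 1.5% | 1.8% | 28% | 0.84 |
| 15 / 30 | 1.4% | 2.4% | 39% | 0.64 |
| 30 / 10 | 2.1% | 1.8% | 50% | 0.74 |
| 30 / 30 | 2.1% | 2.5% | 72% | 0.52 |

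The arm's own interval must be part of the rule. Without it, false claims with a deficit of 0.8 and no change run at 31–48%.

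With two arms, a false claim in at least one occurs in 3.5–4.8% of studies per measure. Over four independent measures that is 1 − 0.965⁴ = 13% to 1 − 0.952⁴ = 18%.

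**The case against.** - **The comparison is planned.** The Lay Summary announces both control comparisons. This stands: a reader might infer that controls were left out of the plan, and the documents do not support that. What is missing is the statistical specification.
- **The tests themselves are sound.** This also stands. A reader might infer that the interaction or the mediation analysis is invalid because controls are absent. The interaction remains a proper randomised comparison of change; only its wording as normalizing is unsupported.
- **Pre-post change is examined first, and the model has a Time factor.** This stands in part. It would be too strong to say that the SAP has no evidence on change, but the Time effect averages the arms, and the only follow-up t-tests named depend on the interaction.
- **Direction is known for task activation.** This stands for that measure. A further fall in activation would not be read as recovery, so it is not true that movement away from controls would pass unnoticed everywhere. The problem is full where no direction is given, as for connectivity. Even for activation, the deficit is not tested in this sample.
- **44% and 75% are simply paired-t power for an assumed shift.** Correct. A reader might take them as the plan's false-claim rate. They are not: they are ungated, and the stricter reading of the SAP gives about 22% and 45%. The low rates under the rule also follow largely from adding a 5% baseline test where the true difference is zero.

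**Conclusion.** The concern holds in this form: the SAP does not specify the control comparisons that the Protocol announces, and none of its models can support normalizing or Hypothesis 1b. The Time × Treatment term and path a support only a difference in change between two active drugs, and the Time effect only an average change. A reader might infer that the SAP at least establishes change due to each drug. It does not: no follow-up scan of controls is described and there is no untreated ADHD arm, so a change within an arm cannot be separated from time or retest effects.

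The conclusion rests on the text and needs no assumed effect size. The illustration (44% or 75% ungated, about 22% or 45% gated) rests on an assumed 0.5 SD shift and r = 0.5. The randomised comparison is unaffected; the headline interpretation is what lacks a test. It should be settled before analysis.

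**What to change.** Keep the existing tests. Add to the SAP, in the same predefined regions and with 95% confidence intervals:

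1. the baseline ADHD-minus-control difference, adjusted for age and sex;
2. each arm's pre-post change, reported whether or not the interaction is significant;
3. each arm's post-treatment ADHD-minus-control difference.

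Use the word normalisation only where the intervals for (1) and (2) exclude zero, the change is toward the control value, and the gap is smaller than before. Otherwise, or if these contrasts are not added, write change. A non-significant result for (3) is not evidence of normalisation.

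Say that the rule applies per arm and per measure (about 2–2.5% false claims each with a deficit of 0.8 SD and no change), and add a multiplicity statement across arms and measures. State which control number applies (10 in the Lay Summary, 30 completers in Description of Subject Population). State also whether pooled controls (Concurrent Research Studies) are used and have the same scan sequences; the Protocol calls the pooled studies' control procedures close to identical but does not list their sequences.

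The cost is SAP wording and added contrasts on scans already planned, since the Protocol has all participants complete the baseline visit with MRI. The downsides should be stated openly. The gap intervals are wide (half-width 0.84 SD for 15 against 10, 0.64 SD for 15 against 30). True partial normalisation (deficit 0.8, shift 0.5 SD) would be claimed in only about 28–72% of studies. Time and retest effects stay unseparated.
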